8.4 Process for Discontinuation of Subject Participation

A Subject is considered enrolled after signing the Informed Consent Document, as described in Section 5.3, Definition of Valid Subject Enrollment. Subject participation may discontinue through screen failure, withdrawal, or death. In all instances of Subject discontinuation after obtaining Informed Consent, an End of Study/Withdrawal eCRF is required to be submitted to the Sponsor supporting the study Subject's study discontinuation/withdrawal.

8.4.1 Preoperative Screen Failures/Withdrawals

A Subject may withdraw consent at any time during the study, even before surgery. The Investigator may withdraw the Subject preoperatively for safety reasons due to eligibility, for example, a patient may become pregnant during the window between giving consent and the planned surgery.

In all instances when a Subject is declared a **screen failure**, the Subject Screening and Enrollment Log must be updated to reflect that Subject's removal/withdrawal from the study. Occasionally, a screen failure (after obtaining consent) will also require and an End of Study/Withdrawal eCRF submitted to DePuy Synthes. Please refer to table 8-5 for further guidance.

Table 8-5: Pre-operative Screen Failure/Withdrawal examples

Screen Failure	Potential Subjects determined to be ineligible for study participation preoperatively, and should not be implanted with study device.		
Example	Action	Follow-Up	
Before consent and before surgery, patient is determined to be ineligible	Update Screening/Enrollment Log as “Screen Failure” and document reason	Do not continue	
After consent and before surgery, Subject is determined to be ineligible	Update Screening/Enrollment Log as “Screen Failure” and document reason Submit Subject History and End of Study/Withdrawal eCRFs to Sponsor	Do not Continue	
Subject Withdrawal	Potential Subject withdraws consent prior to receiving the study implant.		
Example	Action	Follow-Up	
After consent but before surgery, patient withdraws consent	Update Screening/Enrollment Log as “Withdrawal” and document reason Submit Subject History and End of Study/Withdrawal eCRFs to Sponsor	Do not continue	

8.4.2 Intra-operative Withdrawal

The Investigator may withdraw the Subject intraoperatively for safety reasons, for example, it may become clear that the patient is not suited to receive the implant to be used for the study or the surgeon did not use the assigned instruments for whatever reason. Please refer to table 8-6 for further guidance.

Table 8-6: Intraoperative Withdrawal example

Intraoperative Withdrawal: Potential Subjects to be withdrawn from study participation intraoperatively.		
Example	Action	Follow Up
Intraoperatively determined to be ineligible (example, ATTUNE primary implant not suitable)	Update Screening/Enrollment Log as “Intraoperative Withdrawal” and document reason Submit Subject History, and End of Study/Withdrawal eCRFs to Sponsor Inform Subject that they were withdrawn	Do not continue
Example	Action	Follow-Up
Intraoperatively the assigned instruments are not used to perform the proximal tibia and/or distal femoral resections	Update Screening/Enrollment Log as “Intraoperative Withdrawal” and document reason Submit Subject History, Operative Details, Device Log and End of Study/Withdrawal eCRFs to Sponsor. Submit Adverse Event as applicable. Inform Subject that they were withdrawn	Do Not continue
Intraoperatively the ATTUNE implant is attempted but not retained	Update Screening/Enrollment Log as “Intraoperative Withdrawal” and document reason Submit Subject History, Operative Details, Device Log and End of Study/Withdrawal eCRFs to Sponsor. Submit Adverse Event as applicable. Inform Subject that they were withdrawn	Do Not continue

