## 6 Analysis Sets

The determination of subjects to be excluded from the Per Protocol Set will be based on study team review of noncompliance and will be documented separately. The original CIP was written to exclude subjects who had a major protocol deviation, but such deviations may be about study compliance and not necessarily about the scientific integrity of the data. Analysis set definitions from the CIP and those slightly revised definitions per this SAP appear below.

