### 6.1 CIP Analysis Set Definitions

**Consented/Enrolled Population:** All cases consented to participate in this study.

**Safety Population:** All cases that received the Attune device and the assigned instruments were used.

**Per Protocol Population:** All cases from the Safety Population that did not have major protocol violations.

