### 6.2 Modified Analysis Set Definitions

**Consented/Enrolled Set:** All subjects who consented to participate in the study.

**Safety Set:** All subjects who received an ATTUNE device.

Note: If the treatment instrumentation used for the tibial and femoral cuts differ, the subject will be included in the instrumentation group used for the distal femoral cut. If both SUI and RUI were used for a single cut (tibial or femoral), the subject will be included in the first used instrumentation group. The Safety Set will be used to present results for Demographic, Exploratory Endpoints, and Adverse Events.

**Per Protocol Set:** All Safety Set subjects for whom a single instrumentation type was used and who had no protocol noncompliance evaluated which presents serious risk for the validity or integrity of the clinical trial data and/or regulatory acceptability of the sponsor/study/site; safety or well-being of the subject at risk. The Per Protocol Set will be used to present analyses of the primary and secondary endpoints.

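### Protocol Table 8-6 lists for withdrawal implanted knees that SAP 6.2 keeps in the Safety Set, so SAP 8.7 cannot test their exclusion; SAP Per Protocol no longer names the assigned instrument type

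*Protocol*

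**What the plan says.** **Protocol.** The text of 8.4.2 lets the investigator withdraw a subject during surgery if the implant proves unsuitable "or the surgeon did not use the assigned instruments for whatever reason", and refers to Table 8-6 for guidance. The table is firmer. Its heading describes subjects who are to be withdrawn. One row is "Intraoperatively the assigned instruments are not used to perform the proximal tibia and/or distal femoral resections", and its follow-up entry is not to continue. A separate row covers an ATTUNE implant that was attempted but not retained, so this row includes knees that keep the implant. The primary film is taken on day 30 to 150 (Protocol 10.4). AEs are collected until the end of study or withdrawal (Protocol 2, Safety).

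**SAP.** Section 6.1 restates the protocol's Safety Population: "All cases that received the Attune device and the assigned instruments were used". Per Protocol was a subset of it. Section 6.2 replaces this with a Safety Set: "All subjects who received an ATTUNE device". If the tibial and femoral cuts used different types, "the subject will be included in the instrumentation group used for the distal femoral cut". If both types were used for one cut, "the subject will be included in the first used instrumentation group". Per Protocol becomes "All Safety Set subjects for whom a single instrumentation type was used", without serious noncompliance. Section 6 adds: "The determination of subjects to be excluded from the Per Protocol Set will be based on study team review of noncompliance". Section 8.7 repeats the primary analysis in the Safety Population, limited to available data. Nothing is imputed (Protocol 10.5, SAP 8.6).

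**The concern.** The SAP widened the Safety Set and wrote grouping rules for knees that did not get the assigned instruments throughout. The protocol row that sends such knees out of the study was not changed to match. In an open, sequential comparison, failure to use the assigned instruments may itself be a consequence of those instruments. If these knees are withdrawn, they are absent from both Per Protocol and 8.7, and agreement between the two analyses says nothing about them. Their AE record also stops, although the Safety Set is the set for AEs.

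The second part concerns the primary analysis set. Under 6.1, Per Protocol inherited the assigned-instrument condition from the Safety Population. Under 6.2 that condition has gone, and a knee cut wholly with the other type meets the words that replaced it.

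**Working it through.** **1. The plan's own figure.** Inputs from Protocol 10.9 and SAP 7: margin 1.5, SD 1.87, one-sided alpha 0.05, 35 per group. Noncentrality = 1.5 / (1.87 × √(2/35)) = 1.5 / 0.447 = 3.36 on 68 df. The noncentral-t power is 95.3%, which agrees with the stated 95%. Power is 97.2% at 40 per group and 98.2% at 44. Losing a few films therefore costs little power, and the issue is selection.

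**2. Where each kind of knee goes (ATTUNE implant kept).**

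| Knee | In the Table 8-6 row? | SAP Per Protocol | SAP 6.2 Safety Set | Film for 8.7 |
|---|---|---|---|---|
| Tibial and femoral cuts with different types, withdrawn | Yes: one cut was not done with the assigned type | Out | In, by distal femoral cut | None |
| Both types used in one cut, not withdrawn | Not clear | Out | In, by first type used | Yes, if taken |
| Cut wholly with the other type, withdrawn | Yes | No film to analyse | In | None |
| Cut wholly with the other type, not withdrawn | Yes, but not applied | Meets the single-type wording; subject to noncompliance review | In; group not stated | Yes, if taken |

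Rows 1 and 3 show what 8.7 cannot see. Row 2 shows that 8.7 still has something to add. Row 4 is the Per Protocol gap.

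**3. Label in 8.7.** Section 8.7 says Safety Population, the 6.1 name. On the 6.1 definition, knees cut without the assigned instruments are excluded. On the 6.2 definition they are included, but have no film if withdrawn. On either reading, 8.7 cannot test the exclusion of the withdrawn knees.

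**4. How bad the missing knees would have to be.** The number k of missing SUI knees and their mean excess x over the filmed SUI knees are assumptions; the documents give neither.

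The largest observed difference that still passes is 1.5 − t × 1.87 × √(1/n1 + 1/n2):
- 44 v 44: 1.5 − 0.663 = 0.837
- 38 v 44: 1.5 − 0.689 = 0.811

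To find the tipping point, add the k knees back to make 44 v 44. Keep each arm's sum of squares at 43 × 1.87² and add the between-part term for SUI. Then solve for x, where d is the observed difference:

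d + kx/44 + 1.663 × √(V × 2/44) = 1.5, with V = [2 × 43 × 1.87² + (k(44 − k)/44) x²] / 86.

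Check for k = 6, d = 0, x = 5.137: shift = 6 × 5.137/44 = 0.700; V = (300.7 + 136.7)/86 = 5.087; half-width = 1.663 × √(5.087 × 2/44) = 0.800; total 1.50.

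| Missing SUI knees | d = 0 | d = 0.25 | d = 0.5 |
|---|---|---|---|
| 2 | 12.5 | 9.3 | 5.9 |
| 6 | 5.14 | 3.75 | 2.26 |

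(mean excess, in degrees, needed to lose non-inferiority)

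**5. The Per Protocol gap.** Suppose k SUI-phase knees cut wholly with reusable instruments (RUI) were added to 44 RUI knees. The RUI mean would rise by k/(44 + k) × excess. For k = 2 and 1 degree this is 2/46 = 0.04; for k = 6 and 3 degrees it is 18/50 = 0.36. If those knees align like other RUI knees, it is 0.

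**6. Grouping by assigned phase.** If the true difference is 1.5 degrees and k of 44 SUI-phase knees are RUI-cut with RUI-like alignment, the phase grouping shows 1.5 × (1 − k/44): 1.43 for k = 2 and 1.30 for k = 6.

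**The case against.** The case for leaving the text alone has four parts.

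- **The row is guidance.** The 8.4.2 text is permissive, and the table is offered as an example. This stands in part: a reader might infer that every such knee must leave the study, and the text does not establish that. But permissive text beside a firm table lets sites handle the same knee differently, which is a reason to reconcile them.
- **The primary analysis does not need these films.** This stands. Under the protocol's definitions, restated in SAP 6.1, knees cut without the assigned instruments were outside Per Protocol anyway, and withdrawing them was coherent with that. The mismatch arose when the SAP widened the Safety Set.
- **Other barriers exist.** A wholly other-type knee reaches Per Protocol only if the withdrawal row was not applied, a film was taken, and the noncompliance review let it through. This stands, so it would be wrong to call the study-team review the only safeguard. None of these barriers states that the assigned type is required.
- **The effect is probably small.** This stands too. Every surgeon had completed the RUI learning curve before the study (Protocol 7), so knees switched to RUI may align like RUI knees and the effect may be nil.

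The protocol's request for a long-leg film before a revision withdrawal (8.4.5) adds little by comparison. A revision comes later, in a knee that can still belong to Per Protocol, whereas no post-operative weight-bearing film can exist at an intraoperative withdrawal.

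**Conclusion.** There are two wording mismatches, both minor. First, Protocol 8.4.2 with Table 8-6 is not aligned with SAP 6.2 and 8.7: the SAP counts knees in the Safety Set that the table takes out before the film, and the robustness check cannot show the effect of leaving them out. What is affected is the sensitivity analysis and AE collection. Second, SAP Per Protocol has lost the assigned-type condition, which leaves a narrow route into the primary analysis.

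Three stronger readings are not supported. The missing films do not bias the planned Per Protocol analysis as defined. The 8.7 analysis is not empty, because a knee switched within one cut and not withdrawn can enter it. It is not stated that an SUI-phase knee cut wholly with RUI would be counted as RUI, since the grouping note covers only mixed use; the 0.04 to 0.36 degrees above assumes that it would.

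The number of such knees, and the direction and size of any bias, are not in the documents. On the assumptions shown, six missing SUI knees would have to average about 5.1, 3.75 or 2.3 degrees worse to overturn an observed difference of 0, 0.25 or 0.5. A small loss therefore matters only when the result lies near the boundary of about 0.8 degrees.

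**What to change.** 1. Reconcile Protocol 8.4.2 and Table 8-6 with SAP 6.2 and 8.7, so that subjects who keep an ATTUNE implant stay in the study for the already-scheduled film and AE collection whichever instruments were used. They can still be excluded from Per Protocol. The surgeon's choice of instruments is not touched.
2. State in SAP 6.2 that Per Protocol requires the assigned instrument type for both resections.
3. In SAP 8.7, name the 6.2 Safety Set.

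A supportive analysis by assigned phase is optional. If it is added, say that it can dilute a true difference, as shown above.

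The cost is a short protocol amendment, a few lines in the SAP, and a few more films and AE follow-ups of the kind already planned for every subject.

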8.4.3 Enrollment Replacement Rules

Since Subjects are enrolled at the time of consent, any Subject that is withdrawn preoperatively or intraoperatively prior to receiving the study implant will be replaced with subsequent Subjects. Overall, the number of Subjects who received an ATTUNE implant using a study device (with either the RUI or SUI instrumentation), across all sites must meet the sample size of 88.

8.4.4 Postoperative Withdrawal

A postoperative withdrawal is a Subject who has signed the Informed Consent Document, has received an ATTUNE implant using a study device (with either the RUI or SUI instrumentation), and is later withdrawn from study participation (i.e., withdrawal of consent, revision, death, etc.). Please refer to table 8-7 for further guidance.

All data obtained up to the date of withdrawal will be included in the clinical analysis.

Table 8-7: Post-operative Withdrawal Examples

Example	Action	Follow-Up
Subject withdraws consent	
 • Study site documents Subject's request for withdrawal from study. • Complete End of Study/Withdrawal eCRF • Update Screen/Enrollment Log. 	Do not continue
Death	
 • Complete Adverse Event eCRF • Complete End of Study/Withdrawal eCRF • Update Screen/Enrollment Log 	Do not continue
Revision	See Section 8.4.5 and Table 8-8 Revision/Re-Operation Examples	Do not continue if metal tibial base or femoral component revised. Continue to follow if neither the metal tibial or femoral components have been revised.

8.4.5 Revisions / Reoperations

A revision is defined as a surgical procedure of the affected knee where one or more of the TKA components (femoral and/or tibial base, polyethylene insert, or patella polyethylene resurfacing component) are **removed**. Should it be necessary for the Subject to undergo a revision of either the **femoral or metal tibial base components** between the date of the enrollment and the completion of the study data acquisition, **the Subject is to be withdrawn from study participation. Thus, both an Adverse Event (AE) eCRF and an End of Study eCRF would be completed.** If possible, long leg x-rays should be captured prior to revision to permit analysis of the primary objective.

A **re-operation** is defined as any surgical procedure of the affected knee in which **no TKA components are removed**. These subjects are **not to be withdrawn**. An **Adverse Event (AE) eCRF must be completed**. Several examples for revision/reoperations are shown in **Table 8-8**.

Table 8-8: Revision/Re-operation Examples

Revision	
A surgical procedure of the affected knee where one or more of the TKA components (femoral and/or tibial base, polyethylene insert, or patella polyethylene resurfacing component) are removed.
 
If either femoral or metal tibial base components are revised, the Subject is to be withdrawn from study participation.
	
Example	Actions	Follow Up
Removal or revision of either metal tibial base and/or femoral component	Complete Adverse Event eCRF Complete End of Study/Withdrawal eCRF	Do not continue
Tibial polyethylene exchange	Complete Adverse Event eCRF	Continue
Revision of a patella which was resurfaced in the index TKA	Complete Adverse Event eCRF	Continue
Re-operation	
Any surgical procedure of the affected knee in which no TKA components (femoral and/or tibial base, polyethylene insert, or patella polyethylene resurfacing component) are removed.
	
Example	Actions	Follow Up
Irrigation & debridement without tibial insert exchange	Complete Adverse Event eCRF	Continue
Resurfacing of previously unresurfaced patella	Complete Adverse Event eCRF	Continue

8.4.6 Minimization of Subjects Lost to Follow-up

Although follow-up compliance is essential to study quality, some Subjects may not be able or willing to return for follow-up evaluations as prescribed in the protocol. Given the short duration of follow-up in this study, this is not expected to occur often.

Sites should make every effort to ensure complete follow-up whenever possible through phone calls and written requests to a Subject. Each Investigator will maintain a record of communications and/or attempts at communications in the source documentation. This record will be used to obtain an indication or report on the current status of the study device (e.g., still in place and functioning satisfactorily; painful; revised; etc.).

A Subject can be classified as “lost-to-follow-up” and withdrawn from the study only after the visit window has closed and the site has documented in the medical record at least two (2) unsuccessful attempts of contact. Please refer to table 8-9 for further guidance.

Table 8-9: Recommended Contact Attempts

If	Then
A response is not received from phone calls	the Investigator should send a letter to the Subject explaining the follow-up agreement per the informed consent.
A response is not received from the Investigator's letter and/or all attempts to contact the Subject are unsuccessful or the Subject is contacted and chooses to withdraw from the study	the End of Study/Withdrawal eCRF will be completed and will specify why the Subject is no longer participating in this study.

9 RISK ANALYSIS

9.1 Adverse Event Determination

Adverse Event determination will be done by the Principal Investigator, or appropriate designee.

9.2 Non-Reportable Adverse Events - Sponsor ONLY

There are immediate post-operative events that are changes from the baseline condition of the Subject, but are expected events resulting from the surgery. If these events occur, they should be recorded in the Subject's medical record per standard medical practice, but it is not necessary to report them as AEs in the eCRF or to the Sponsor (please refer to Exhibit E-2 for listing of Non-reportable AEs).

9.3 Study Related Risks / Reportable Adverse Events

Any surgical procedure poses a potential risk and the procedures undertaken as part of this clinical investigation are no exception.

The surgical risks associated with the use of the Single Use Instruments for implanting the ATTUNE cemented primary TKA system are similar to those with the Re-usable instruments for implanting the ATTUNE cemented primary TKA system when used for the same clinical indication. Additionally, the surgical risks are the same whether or not the Subject participates in this study for a number of reasons:

- It is assumed that the Investigator and patient have mutually decided that primary TKA is an appropriate treatment for the patient's condition and that the patient would have a TKA whether or not they choose to take part in this study;
- The same implant is used with both RUI and SUI instrumentation;
- Both types of instruments have to meet the same design control requirements/standards prior to market availability as do all surgical instruments on the market;
- Participating Investigators in this study are already implanting the ATTUNE TKA system with the re-usable instruments and will obtain training on the single use instruments prior to enrolling study Subjects.

Study related risks are categorized as those anticipated to be related to general surgical risks, total knee arthroplasty risks, or those potential risks associated with the study implant system. Unanticipated Adverse Events may occur as well.

This protocol requires each site to report AEs, SAEs, ADEs, and SADEs to their respective IRB/EC per their IRB/ECs respective requirements

A summary of risks is described below, please refer to the printed IFU for additional details (Exhibit D).

A. General Surgical Risks

Confidential
Revision Date: 19Feb-2018

DePuy Synthes Joint Reconstruction
Protocol: CIP 10002 REV B

General surgical risks and post-operative adverse events can occur with any surgery and include, but are not limited to:

- Anesthetic complications/reactions
- Bleeding and/or excessive blood-loss
- Transfusion reaction
- Post-operative infection
- Vascular injury
- Delayed wound healing
- Deep vein thrombosis (DVT)
- Nerve injury
- Death

B. Risks Associated with Total Knee Arthroplasty Procedure/Study Device/Instruments

Potential adverse events associated with primary total knee arthroplasty include, but are not limited to:

- Early or late loosening of the prosthetic component(s)
- Tibial subsidence
- Bending, cracking, fracture, deformation of the prosthetic components
- Excessive wear of the polyethylene articulating surface
- Progressive bone resorption (osteolysis) as a result of foreign-body reaction to wear debris
- Early or late infection
- Delayed wound healing or wound dehiscence
- Pain
- Dislocation or joint instability of the knee
- Subluxation of the knee
- Flexion contracture
- Varus-valgus deformity
- Malalignment
- Decreased range of motion
- Leg length discrepancy
- Soft tissue impingement or damage
- Bone fracture(s)
- Nerve damage
- Localized swelling
- Vascular injury
- Temporary or permanent neuropathies
- Cardiovascular disorders including venous thrombosis, pulmonary embolism, or myocardial infarction
- Histological reactions resulting in inflammation
- Metal sensitivity
- Corrosion of metal components (the significance and long-term implications are uncertain and await further clinical evidence and evaluation)
- Re-usable or single use instrument breakage

